3.2.2 Urine Tests

Participants will provide a spot urine sample for quantification of albumin/creatinine ratio and protein/creatinine ratio at 4 of the trial days. As well as four 24 hour urinary collections on the days prior to the renal physiological tests days.

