3.2.3 Renal Physiological Tests

Participants will attend the Clinical Research Centre (CRC) on 4 separate trial days (2 while in each arm of the trial). On each trial day, participants will present themselves to the CRC, following an overnight fast. Two days before presenting to the CRC, participants will be required to follow a 2gm sodium and 2L fluid/day controlled diet. A 24-hour urine collection will be made in the 24 hours prior to the day of the renal physiological test. Participants will be asked to take their morning usual medications except their IMP (empagliflozin or placebo) and furosemide (or equivalent loop diuretic).

[figure not shown]
An intravenous cannula will be placed in each arm for subsequent infusion and blood sampling. Bloods will be drawn for measurement of plasma NT-proBNP (a biomarker of wall stress and will be measured as a discovery variable in this proof of concept trial) using standard protocols. Firstly, a 15 ml/kg oral water load will be administered over approximately a 15-minute period. Thereafter, at approximately 30 minute intervals, participants will be requested to void urine until the end of the trial day. The volume of urine passed will be measured and an aliquot stored for later analysis. On each occasion, the volume of urine passed will be measured, and an equal volume of water given to drink. In this way, a steady state diuresis will be established over approximately 3 hours. The last urine collection during this stabilization period will be taken as baseline. Approximately 3 hours after initiation of the test, each participant will receive an oral tablet of either empagliflozin 25mg or placebo. After the seventh urine sample, participants will be given a bolus of IV furosemide at half their total daily dose. Heart rate will be displayed continuously on an ECG oscilloscope and the blood pressure measured approximately every 60 minutes. Venous blood will be obtained at the midpoint of each clearance period for measurement of serum sodium, osmolality and creatinine. At the end of the RPT, light refreshments in the form of tea, coffee or juice with biscuits will be provided. A lunch will then be provided at the CRC.

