9.3 MISSING DATA

The primary analysis will be based on the intention-to-treat principle. The extent of missing data will be examined and the reason for the dropout ascertained. Multiple imputation may be used to impute missing values if necessary and where assumptions for missing at random (MAR) data are met. Complete case analysis where missing participants are excluded will be carried out as a secondary analysis. Pre-specified sub-group analyses will be completed by fitting the appropriate interaction term in the regression model and- if significant outcomes will be presented separately by level of sub-group.

With regards to participant medication, this will be recorded at baseline and at each trial visit with a secondary analysis adjusting for changes in trial medications planned.

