### 5.4 Study Variables

The primary end point was analysed as the total volume of urine from the 24 hour urine collection at the end of treatment.

Statistical Analysis Plan: RECEDE-CHF trial

Visit	Visit 1* Screening	Visit 2* Baseline/ Randomisation	Visit 3	Visit 4 (Tele Visit)	Visit 5	Two week wash-out period	Visit 6	Visit 7	Visit 8 (Tele Visit)	Visit 9 ****	Visit 10 (Final visit)
	Up to 4 weeks pre visit 2	Day 0	Day 3 (+/-2 days)	Week 3 (+/- 3 days)	Week 6 (+/- 3 days)		Week 9 (+/- 3 days)	Week 9 + 3 days (+/- 2 days)	Week 12 (+/- 3 days)	Week 15 (+/- 3 days)	Week 19 (+/- 7 days)
Height	X										
Weight	X	X	X		X		X	X		X	X
Vital Signs – blood pressure & pulse	X	X	X		X		X	X		X	
Safety Bloods	X	X	X		X		X	X		X	
HbA1c	X				X		X			X	
Research Bloods		X	X		X		X	X		X	
Urine sample	X	X	X		X		X	X		X	
24 hour urinary collection			X		X			X		X	
Renal Physiology Test			X		X			X		X	

Table 1: Trial schedule for RECEDE-CHF

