## **7.3 Covariates and Subgroups**

Covariates that may have an influence on the end points listed include gender, BMI, age and treatment order received i.e. placebo/empagliflozin versus empagliflozin/placebo. As the study is a crossover in design, the treatment order was included in the initial analysis as a covariate to ascertain if the intervention being investigated has a sustained effect on the primary outcome despite the 2 week washout period. These demographic subgroups were analysed for different treatments effects (for example comparison of effects by age, gender, BMI and treatment order). Where possible forest plot figures were used to communicate the relevant information about possible subgroup effects and interactions.

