### **9 Efficacy Analyses**

Efficacy analysis was performed on the intention to treat population as defined in section 7.2.

Data for continuous outcome measures were assessed for normality prior to analysis. Transformation of the outcome variables was used where necessary where these were not normally distributed. Outcome measures were assessed by 2 way Analysis of Variance (ANOVA). Initial comparison was between treatment groups (empagliflozin

vs placebo) at the final visit of each treatment arms (visit 5 and visit 9) adjusted for baseline measures (visit 2 and visit 6) of the outcomes.

Where data was not normally distributed and could not be transformed into a normal distribution, data were analysed using non–parametric methods. Data for categorical outcomes measures were assessed by logistic regression in the same way as described for continuous outcome measures.

All efficacy variables were listed by subject within study centre. Data were summarised by treatment group. Number, Mean, Standard Deviation, Minimum and Maximum will summarise continuous efficacy variables, whereas number and percent will summarise categorical efficacy variables.

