## 9.1 Primary Efficacy Analysis

The primary outcome measure was analysed in the same manner as described above and presented as the between treatment group difference in change in urine volume between the baseline and final visits.

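### SAP 9 and 9.1 call for a visit 2/6 baseline that is never collected for the primary 24-hour urine volume; the 2-way ANOVA also leaves its participant and period terms unnamed

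*SAP*

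**What the plan says.** **Endpoint.** SAP 5.4: "The primary end point was analysed as the total volume of urine from the 24 hour urine collection at the end of treatment".

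**Baseline.** SAP 9 compares the treatments at visits 5 and 9, "adjusted for baseline measures (visit 2 and visit 6) of the outcomes". SAP 9.1 presents the primary result as the "between treatment group difference in change in urine volume between the baseline and final visits". SAP 9.2 analyses the secondary outcomes in the same way, including sodium from the 24-hour collection.

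**Collections.** Protocol 3.2.2 plans "four 24 hour urinary collections on the days prior to the renal physiological tests days". Protocol 3.2.3 agrees: "A 24-hour urine collection will be made in the 24 hours prior to the day of the renal physiological test". SAP Table 1 and Protocol Appendix 1 mark these collections at visits 3, 5, 7 and 9.

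**Model.** SAP 9: "Outcome measures were assessed by 2 way Analysis of Variance (ANOVA". The only factor named there is treatment. SAP 7.3 adds that "the treatment order was included in the initial analysis as a covariate to ascertain if the intervention being investigated has a sustained effect", and lists treatment order among the subgroups. Protocol 9.3: "Pre-specified sub-group analyses will be completed by fitting the appropriate interaction term in the regression model"; where the interaction is significant, results are shown separately by subgroup level. In the SAP, a repeated-measures ANOVA is named only for the renal test days (9.2).

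**The concern.** A stated rule for the primary analysis depends on measurements that the trial does not schedule. The analyst would have to improvise, and the choices do not estimate the same quantity. The end-of-treatment comparison in SAP 5.4 estimates the week-6 effect. A change from visit 3 or 7 would estimate the week-6 effect minus the day-3 effect.

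The model is also open. In an AB/BA crossover, the participant term sets the standard error, and the period term protects the estimate when the analysed sequences are unequal. SAP 9 names neither. The one crossover term that is stated, treatment order, is constant within a participant.

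**Working it through.** **1. Baselines required and baselines scheduled**

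| Outcome | Source at visits 2 and 6 | Baseline available? |
|---|---|---|
| 24-hour volume (primary) | no collection; visits 3, 5, 7, 9 only | no, 0 of 2 |
| 24-hour sodium | no collection; visits 3, 5, 7, 9 only | no, 0 of 2 |
| eGFR, creatinine | safety bloods | yes |
| Cystatin C | research bloods | yes |
| Protein/creatinine and albumin/creatinine ratios | spot urine | yes |

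The gap is in the design, so multiple imputation (SAP 7.4) has no observed visit 2 or 6 volume to work from. The spot urine at those visits is for the two ratios. The baseline mentioned in Protocol 3.2.3 is a void within the test day.

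**2. If visits 3 and 7 were used instead**

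These visits are about 3 days (±2) into each treatment period. Let E be the week-6 effect and d the day-3 effect. The between-treatment difference in change is E − d. With d assumed to be 0, 50% or 100% of E, the share of the effect that remains is 100%, 50% or 0%.

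**3. What treatment order can and cannot supply**

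The plan's own inflation reproduces: 22/(1 − 0.35) = 33.8, so 34 randomised. I use 22 completers with both visits. Ranks of the design matrix:

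- Treatment + order: rank 3. Adding period gives 4, so order does not carry period.
- Participant + treatment: rank 23. Adding order leaves 23, so order is only one contrast between participants and does not replace the participant term.
- Treatment + order + treatment-by-order: rank 4. Adding period leaves 4, so the interaction is aliased with period.

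**4. Leaving out participant (no period effect)**

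The true variance of the treatment difference is 2σ²(1 − ρ)/n. Ignoring pairing uses 2σ²/n. The standard error is therefore too large by 1/√(1 − ρ): 1.20, 1.41 and 1.83 at assumed ρ of 0.3, 0.5 and 0.7. Simulated two-sided type I error at nominal 5% (11/11) is about 2%, 0.7% and 0.1%.

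**5. Leaving out period, with or without participant**

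Let π be period 2 minus period 1 and τ the treatment effect. The expected treatment difference is τ − π in sequence AB (empagliflozin first) and τ + π in BA. Pooling gives τ + π(n_BA − n_AB)/n. Treatment + order without participant gives the same point estimate, because every completer contributes both treatments.

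| Assumed AB/BA split | Size of bias as share of π |
|---|---|
| balanced | 0 |
| 18/16 of 34 | 2/34 = 6% |
| 12/10 of 22 | 2/22 = 9% |
| 14/8 of 22 | 6/22 = 27% |

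At 14/8, an assumed π of 0.4 SD gives a bias of −0.11 SD, and 0.8 SD gives −0.22 SD. In the 0.8 SD case, simulated type I error for treatment + order without participant is 7–8% at ρ of 0 to 0.1 and about 5% at ρ of 0.3. So that reading is not always conservative. Weighting the two sequences equally gives ½[(τ − π) + (τ + π)] = τ, with no bias.

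**6. Treatment-by-order as a subgroup**

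The by-order estimates differ by (τ + π) − (τ − π) = 2π. With 22 completers (11/11) and ρ of 0.5, a pure period effect of 0.2 or 0.4 SD makes this interaction significant in about 15% or 43% of simulated trials. Protocol 9.3 would then show the treatment effect separately by order.

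**The case against.** **The baseline sentence is general.** SAP 9 writes it for all outcomes, it works for five of the seven, and SAP 5.4 gives a primary endpoint that needs no baseline. This stands as a limit on scope. It does not remove the contradiction, because SAP 9.1 applies the change wording to urine volume itself.

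**Correct models are within the wording.** Visits 5 and 9 are the two period ends, so treatment + visit + participant is a fair reading of a 2-way ANOVA. A paired treatment-by-order analysis with sequences weighted equally is another. Protocol 9.2.1 refers to ANOVA for repeated measurements, which favours a within-participant analysis. This stands: the second part is under-specification. A reader might infer that a wrong model was fitted; the documents do not show that.

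**The bias needs imbalance.** Block randomisation and the intention-to-treat set should keep the sequences close to equal, and Protocol 5.5.4 replaces withdrawals where possible. The larger splits belong to the complete-case analysis, which Protocol 9.3 makes secondary. This also stands. The block size, any period effect and the final split are not given.

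**Use of visits 3 and 7 is a possibility only.** Nothing in the SAP points to them. Used as a covariate rather than in a change score, they would not subtract the day-3 effect one for one.

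**Power loss.** A reader might convert the larger standard error into lost power against the planned 90%. That 90% was set for furosemide-induced volume (Protocol 9.1.1, SAP 6). Neither document gives an SD or mean for 24-hour volume, so no power figure for this endpoint is supported.

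**Conclusion.** The baseline problem holds on the documents alone and needs no assumption: the adjustment in SAP 9 and the change in SAP 9.1 cannot be computed for 24-hour volume or 24-hour sodium, and they conflict with the endpoint in SAP 5.4. It should be fixed.

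The model point is secondary, an ambiguity to close. Treatment order as a main effect gives neither pairing nor period, and the planned by-order subgroup would display a period effect as if it were effect modification. The sizes rest on assumed values of ρ, the period effect and the split: a standard error 1.20 to 1.83 times too large without participant when there is no period effect, and a bias of 0 to 27% of the period effect without period.

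Two stronger conclusions are not supported: that leaving out participant is always the safe direction, and that the reported result is invalid.

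**What to change.** - **24-hour volume and 24-hour sodium:** delete the baseline adjustment and the change-from-baseline wording. Compare end-of-treatment values at visits 5 and 9, as SAP 5.4 says. State that visits 3 and 7 are on treatment and are not baselines.
- **Other outcomes:** keep the visit 2/6 adjustment for eGFR, creatinine, cystatin C and the two urine ratios.
- **Model:** in SAP 9, name treatment, period and sequence as fixed effects and participant as random, and report the treatment difference with a 95% confidence interval.
- **Treatment-by-order:** report it as the period estimate and remove it from the subgroups in SAP 7.3.

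The cost is SAP wording and about 1 degree of freedom (with 22 completers, 20 residual instead of 21 once period is added). Much of the SAP is in the past tense. If the analysis is already complete, document the model that was fitted and how baseline was handled, and label any re-analysis as post hoc.

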3 TRIAL DESIGN

3.1 TRIAL DESCRIPTION

The RECEDE-CHF Trial is a single centre randomised, double-blind, placebo-controlled, crossover, trial conducted in NHS Tayside to compare the SGLT2 inhibitor empagliflozin 25mg, to placebo. Participants will be enrolled in the trial for a period of between 14 to 16 weeks.

At the screening visit, following informed consent, an initial medical history and clinical examination will be performed and concomitant medication will be recorded. Participants will have bloods taken for safety analysis and vital signs will be checked to confirm eligibility prior to enrolment. An assessment of suitability of the trial for the potential participant will be undertaken by the principal investigator or medically qualified delegate.

Should the participant meet the inclusion criteria and have no exclusion criteria identified, they will return for the baseline/randomisation visit at the Clinical Research Centre (CRC), Ninewells Hospital, Dundee, within four weeks post screening visit. Where possible the screening visit and randomisation visits will be combined.

At the randomisation visit participants will undergo safety blood tests, vital signs and trial medication will be dispensed (either empagliflozin 25mg or placebo).

Participants will continue on trial medication, empagliflozin 25mg or placebo, once daily, for a period of 6 weeks. Participants will be educated on the symptoms of hypoglycaemia which includes a written action plan on how to manage it in the unlikely event that it occurs.

Participants will return to the CRC 3-days (±2 days) post-randomisation, for a trial day, lasting approximately 5 hours, where they will have safety and research bloods drawn, vital signs recorded and will undergo renal physiological tests (RPT). Participants will be required to provide several urine samples throughout the course of the visit.

Participants will then return again at week 6 for a trial day, lasting approximately 5 hours, where they will undergo RPT again, safety and research bloods will be drawn and vital signs recorded. Participants will be again required to provide several urine samples throughout the course of this visit. Participants will terminate trial drug, either empagliflozin 25mg or placebo, at this visit and will return to the CRC at the end of the two week wash out period (week 9)

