## **7.4 Missing Data**

Missing values represent a potential source of bias in a clinical trial. Therefore every effort should be undertaken to fulfil all requirements of the protocol concerning the collection and management of data. The extent of the missing data was examined and the reason for drop–out ascertained. Multiple imputation was used to impute missing values where necessary and where assumptions for missing at random (MAR) data were met.

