### **8.3 Demographic and Baseline Variables**

Demographic variables that were recorded at the screening visit prior to randomisation were:

- Age
- Gender
- Concurrent Illnesses and Medical Conditions
- BMI
- Smoking history
- Alcohol intake (units/week)
- Severity of heart failure as identified by the ejection fraction (mild, moderate or severe) on echocardiogram
- Medication classes

All baseline variables that were recorded at the screening visit prior to randomisation include:

- blood pressure
- pulse
- weight
- BMI

- HbA1c
- eGFR
- Serum creatinine
- Urine Protein/Creatinine Ratio
- Urine Albumin/Creatinine Ratio

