## 9.2 Secondary Efficacy Analyses

All secondary outcomes were analysed in the same manner as the primary outcomes. Results were presented as:

- between treatment group difference in urinary sodium excretion, from the 24 hour urinary collection
- between treatment group difference in estimated glomerular filtration rate (safety endpoint)
- between treatment group difference in serum creatinine (safety endpoint)
- between treatment group difference on protein/creatinine ratio
- between treatment group difference on albumin/creatinine ratio

- between treatment group difference on the renal biomarker, cystatin C.

In analysing the results from the Renal Physiology test days, these will be analysed via a 2 way repeated measures ANOVA for both urinary volume and urinary sodium.

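### The primary analysis needs a baseline 24-hour urine volume at visits 2 and 6, and the schedule collects none

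*SAP*

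**What the plan says.** SAP 5.4 fixes the primary variable: "The primary end point was analysed as the total volume of urine from the 24 hour urine collection at the end of treatment". SAP 9 then sets out the efficacy model. Outcomes are compared between treatments at the last visit of each period (visits 5 and 9), "adjusted for baseline measures (visit 2 and visit 6) of the outcomes". SAP 9.1 applies that model to the primary outcome, with the result "presented as the between treatment group difference in change in urine volume between the baseline and final visits". SAP 9.2 carries it over to the other outcomes: "All secondary outcomes were analysed in the same manner as the primary outcomes". One of those is urinary sodium from the same 24-hour collection.

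SAP Table 1, in section 5.4, marks the 24-hour collection at visits 3, 5, 7 and 9. Protocol 3.2.2 gives four such collections, each tied to a renal physiological test day. Protocol 3.2.3 places two test days in each arm, and SAP 5.1 places them in the first and last week of each treatment period.

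**The concern.** Read together, SAP 5.4, 9 and 9.1 require a 24-hour urine volume at visit 2 and again at visit 6. The trial's own schedule has no collection at either visit. The primary result cannot then be produced in the form the SAP states.

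The analyst would have to choose a replacement: no baseline at all, visits 3 and 7 as baselines, or a void from the renal test day. These estimate different quantities, and the SAP does not say which applies. An SAP is meant to settle such a choice before the blind is broken. SAP 9.1 also disagrees with SAP 5.4 on form, because one reports a change and the other an end-of-treatment value.

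**Working it through.** **Reproducing the plan's own count.** Reading the 24-hour row of SAP Table 1 column by column gives visits 3, 5, 7 and 9. That is four collections per participant, as protocol 3.2.2 states. None falls at visit 1, 2 or 6.

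The same row in protocol Appendix 1 has lost its wash-out column in the machine-read text, so it is not relied on. Aligned in the same way as the drug-dispensing row, which then falls at visits 2 and 6, it gives the same four visits. Read without that alignment, it would put a renal test on the visit 8 telephone call.

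**Counts.** Inputs are 34 participants, two periods and 35% drop-out (SAP 6; 22 / 0.65 = 33.8, rounded up to 34).

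- Baseline volumes required: 34 x 2 = 68. Scheduled at visits 2 and 6: 34 x 0 = 0.
- All scheduled collections: 34 x 4 = 136.
- Collections at the final visits 5 and 9: 34 x 2 = 68.
- Completers: 34 x (1 - 0.35) = 22.1, so about 22. They give 22 x 2 = 44 final-visit values and still 0 baselines. This assumes that drop-outs contribute nothing and are not replaced.

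**Which outcomes are affected.** There are 1 + 6 = 7 listed outcomes.

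| Outcome | Source | Scheduled at visits 2 and 6? |
|---|---|---|
| 24-hour urine volume (primary) | 24-hour collection | No |
| 24-hour urinary sodium | 24-hour collection | No |
| eGFR, serum creatinine | Safety bloods | Yes |
| Cystatin C | Research bloods | Yes |
| Protein/creatinine and albumin/creatinine ratios | Urine sample | Yes in both visit schedules, but protocol 3.2.2 limits spot samples to four trial days |

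Two outcomes have no baseline, three clearly have one, and two have one if the schedules prevail over protocol 3.2.2.

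**Possible substitutes.**

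- *The visit 2 and visit 6 urine sample.* Appendix 1 assigns it to the two ratios. It gives no 24-hour volume.
- *Visits 3 and 7.* SAP 9 does not name them. They fall 3 days (±2) after dispensing, so their collections follow or overlap the start of dosing. Adjusting for them could remove part of the treatment effect.
- *The baseline void of protocol 3.2.3.* It covers about 30 minutes after a water load, on a test day within a treatment arm. It is a different variable and is not pre-treatment.
- *Imputation.* SAP 7.4 says "Multiple imputation was used to impute missing values where necessary". A quantity observed in no participant gives an imputation model nothing to work from.

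**The case against.** The strongest counter-argument is that little is lost. In a crossover each participant is scheduled for both treatments, so the within-participant contrast of visits 5 and 9 needs no baseline, and SAP 5.4 already defines the endpoint that way. The sentence in SAP 9 is written for all outcomes and works for most of them. No bias, error-rate or power consequence has been shown. All of this is right, and it limits the damage to what the SAP says rather than what the trial can estimate. It does not rescue SAP 9.1, which names urine volume and change from baseline specifically for the primary outcome.

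Some supporting evidence is weak and should carry no weight. Protocol 3.1 says "At the randomisation visit participants will undergo safety blood tests, vital signs and trial medication will be dispensed" and mentions no urine collection, but that narrative also omits research bloods that are scheduled at the same visit. The list in SAP 8.3 ("All baseline variables that were recorded at the screening visit prior to randomisation include") has no urine volume, but it concerns screening, is not worded as exhaustive, and leaves out cystatin C as well. SAP Table 1 with protocol 3.2.2 and 3.2.3 carries the point alone.

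It would also be too strong to say that every collection is wholly on treatment. If visit 3 or 7 falls one day after dispensing, its 24-hour collection could straddle the first dose. That does not make it a usable baseline.

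**Conclusion.** The concern holds. For 24-hour urine volume, 0 of the 2 baseline measurements that SAP 9 requires per participant are scheduled (0 of 68 overall, before drop-out). The baseline adjustment and the change-from-baseline primary result cannot be computed, and the same is true of 24-hour sodium. This is a stated primary analysis that the design cannot deliver, so it must be corrected.

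The treatment effect itself can still be estimated from visits 5 and 9. No power or bias figure is attached, because the documents do not support one for this defect. The conclusion rests on SAP Table 1 being the operative schedule, which protocol 3.2.2 and 3.2.3 confirm.

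**What to change.** - **SAP 9:** limit the visit 2 and visit 6 adjustment to outcomes measured at those visits: eGFR, serum creatinine, cystatin C and, once protocol 3.2.2 is reconciled with the visit schedules, the two urine ratios.
- **SAP 9.1:** replace the change from baseline with the within-participant empagliflozin minus placebo difference in end-of-period 24-hour volume (visits 5 and 9), in line with SAP 5.4. Since the model sentence is being rewritten, state that it accounts for participant and period, as the crossover requires, and keep the term in SAP 7.3, under which "the treatment order was included in the initial analysis as a covariate".
- **SAP 9.2:** say that 24-hour sodium is analysed the same way, without a baseline.
- State that visits 3 and 7 are not baselines for the primary comparison.

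This takes the SAP 5.4 endpoint as given. The protocol's professional summary and both sample-size sections refer instead to the urine-volume response to furosemide. That mismatch is separate; if it is settled in favour of the furosemide response, SAP 9.1 must be revised again.

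The cost is SAP wording only, with no new visits or data. The SAP is largely in the past tense, so if the analysis has already been run, the change should appear as a dated amendment or a disclosed deviation.
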